5.1 Cohort Summary

This study will involve a new user, parallel group, propensity score-matched, retrospective cohort study design comparing 15-minute annual infusions of zoledronic acid (5mg) to raloxifene (as a proxy for placebo). Raloxifene was selected as the placebo proxy because raloxifene was the most common concomitant osteoporosis medication used in the trial in both study arms. In addition, prior evidence indicates no effect of raloxifene on the primary outcome of hip fracture (Ettinger et al., 1999, Ensrued et al., 2008). The patients will be required to have continuous enrollment during a baseline period of 450 days (15 months) before initiation of zoledronic acid or comparator. We will restrict the analyses to women, older than 65, with osteoporosis.

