1.5 Secondary endpoint for replication (assay sensitivity) and RCT finding

Non-vertebral fracture

1.6 Trial estimate

Hazard Ratio, HR = 0.59 (95% CI, 0.42 to 0.83) comparing zoledronic-acid group vs. placebo group during a 3-year period (Black et al., 2007).

Note. The follow-up period of the RWE replication is set at 18months. In the trial, the HR comparing zoledronic-acid group vs. placebo group during an 18-month period is estimated to be ~ 0.745 . The HR at 18 months is defined as the ratio between the cumulative incidences of hip fracture events in the zoledronic-acid and placebo groups ($HR = \frac{CI_{ZA}}{CI_{placebo}}$) measured after 18 months of follow-up. The estimates of the cumulative incidences of hip fracture events have been extracted by the Kaplan-Meier curves reported in the trial using a dedicated software (Graph Grabber 2.0.2, Quintessa Ldt).

2. Person responsible for implementation of replication in Action

[name], MPH, implemented the study design in the Aetion Evidence Platform. She is not responsible for the validity of the design and analytic choices. All implementation steps are recorded, and the implementation history is archived in the platform.

3. Data Source(s)

Optum CDM, IBM® MarketScan®

4. Study Design Diagram

The study design diagram visualizes key aspects of the longitudinal study design for expedited review.

Cohort Entry Date (Day 1) [Dispensation of Zoledronic acid (5 mg, IV administered annually)] OR [Raloxifene (oral tablet administered daily)] INCL: Diagnosis of Osteoporosis Days [Enrollment, 0] **INCL**: Use of meds for osteoporosis INCL: Age ≥ 65 Days [0] EXCL: Amputation or absence of lower limb Days [Enrollment, 0] EXCL: Prior use of Bisphosphonate OR parathyroid hormon Days [-730, 0] EXCL: Treatment and Prevention of Glucocorticoid-Induced Osteoporosis Days [-730, 0] EXCL: Treatment of Paget's Disease of Bone Days [-730, 0] Days [-450, 0] EXCL: Life expectancy less than 6 months (CCl ≥ 10)

Days [-450, 0] EXCL: Malignant neoplasms Days [-365, 0] ons that influence bone metabolism (e.g frome, Anorexia, bulimia, RA, SLE, IBD, hyperthyroidism, etc.) Days [-365, 0] EXCL: conditions/circumstances likely to lead to poor treatment adherence (Alcohol/drug abuse)

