5.2 Important steps for cohort formation

New use of zoledronic acid (exposure) is defined as no use of the exposure drug in the 450 days prior to index date. New users of zoledronic acid will be allowed to receive concomitant therapy with raloxifene before and/or during the study period, similar to the trial. We use the long look-back period of 450 days to define new use because zoledronic acid is given as a yearly infusion; thus, a identifying whether a patient has current zoledronic acid exposure requires at least 365 days of look back. We extended this lookback to 450 days (approximately 15 months) to allow for patients who have a short gap between infusions. To keep the amount of lookback available in the 2 treatment groups equal, New use of raloxifene (comparator, proxy to placebo) was also defined as no use of either exposure or comparator drugs in the 450 days prior to index date.

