5.3 Flowchart of the study cohort assembly

For zoledronic acid vs. raloxifene

	Optı	ım CDM	IBM® Ma	rketScan®
	Excluded Patients	Remaining Patients	Excluded Patients	Remaining Patients
All patients		77,673,639		200,203,908

	-77,476,067	197,572	-	489,107
Did not meet cohort entry criteria			199,714,801	
Excluded due to insufficient enrollment	-52,317	145,255	-164,242	324,865
Excluded due to prior use of referent	-81,791	63,464	-185,458	139,407
Excluded due to prior use of exposure	-9,268	54,196	-29,153	110,254
Excluded because patient qualified in >1 exposure category	-1	54,195	-1	110,253
Excluded based on Inclusion #1 - Age, range 65-89 years	-17,914	36,281	-58,739	51,514
Excluded based on Inclusion #2 - Gender, female [Excluded if Male or Unknown]	-6,080	30,201	-6,857	44,657
Excluded based on Inclusion #3 - Osteoporosis	-3,624	26,577	-3,936	40,721
Excluded based on Exclusion #1 - Oral bisphosphonate use	-6,854	19,723	-10,259	30,462
Excluded based on Exclusion #2.1 - PTH or PTH analogue use	-305	19,418	-814	29,648
Excluded based on Exclusion #2.2 - Anabolic–androgenic steroids (AAS) and	-10	19,408	-32	29,616
growth hormones (GH)				
Excluded based on Exclusion #2.3 - Glucocorticoids use	-1,352	18,056	-1,697	27,919
Excluded based on Exclusion #3 - CCI (180 days) >=10	-196	17,860	-154	27,765
Excluded based on Exclusion #4 - Malignant neoplasm, excluding non-melanoma	-2,461	15,399	-4,141	23,624
skin cancer				
Excluded based on Exclusion #5 - Disorders that influence bone metabolism	-1,426	13,973	-2,235	21,389
Excluded based on Exclusion #6 - Glucocorticoid-Induced Osteoporosis	-4	13,969	-5	21,384
Excluded based on Exclusion #7 - Paget's Disease	-43	13,926	-65	21,319
Excluded based on Exclusion #8 - Alcohol abuse or Drug addiction or Non-	-141	13,785	-137	21,182
compliance	1	10.504	2	21 170
Excluded based on Exclusion #9 - Pregnancy	-1	13,784	-3	21,179
Excluded based on Exclusion #10 - Lower extremity amputation	-18	13,766	-37	21,142
Excluded based on Exclusion #11 - Denosumab use	-53	13,713	-35	21,107
Excluded based on Exclusion #12 - Zoledronic Acid use (for raloxifene users)	-223	13,490	-313	20,794
Excluded based on Exclusion criteria #13 - End-stage renal disease	-5	13,485	-12	20,782
Excluded based on Exclusion criteria #14 - End-stage liver disease	-33	13,452	-66	20,716
Excluded based on Exclusion criteria #15 - Blindness or low vision	-32	13,420	-25	20,691
Excluded based on Exclusion criteria #16 - Abaloparatide	-0	13,420	-0	20,691

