2	Bone mineral density T score of -2.5 or less at the femoral neck, with or without evidence of existing vertebral fracture, or a T score of -1.5 or less, with radiologic evidence of at least two mild vertebral fractures or one moderate vertebral fracture.	Measured time of enrollment to prior to the day of drug initiation inpatient (any position), outpatient (any position): Osteoporosis diagnosis ICD-9 diagnosis: 733.00, 733.01, 733.02, 733.03, 733.09, 733.13 ICD-10 diagnosis: M81.0, M81.6, M81.8, M80.88*, M80.08* OR Measured time of enrollment to 730 days (2 years) prior to the day of drug initiation: Alendronate, Ibandronate, Risedronate, Pamidronate, Etidronate, Tiludronate		Adequate mapping in claims of criteria extracted from clinicaltrial.gov (ESLD and Svere eye disease), after clinical review with FDA (Abaloparatide, Romosozumab) or from the protocol of Horizon-recurrent (all other criteria in blue): "Colôn-Emeric CS, Caminis J, Suh TT, Pieper CF, Janning C, Magaziner J, Adachi J, Rosario-Jansen T, Mesenbrink P, Horowitz ZD, Lyles KW; HORIZON Recurrent Fracture Trial. The PHORIZON Recurrent Fracture Trial: the prevention of subsequent fractures after low trauma hip fracture repair. Curr Med Res Opin. 2004 Jun;20(6):903-10. doi: 10.1185/03079904125003683. PMID: 15200749." Protocol of Horizon-pivotal not available - numerous unsuccessful attempts had been made to retrive it from the authors	

	EXCLUSION	CRITERIA	
1	Bisphosphonate users such as Aredia® (pamidronate), Didronel® (etidronate), Fosamax® (alendronate), Actonel® (risedronate), Skelid® (tiludronate)	Measured 730 days (2 years) prior to the day of drug initiation: Generic names: Alendronate, Ibandronate, Risedronate, Pamidronate, Etidronate, Tiludronate	
2.1	Previous use of: (1) any previous use of parathyroid hormone	Measured 730 days (2 years) prior to the day of drug initiation: Generic names: Brand names: Natpara® (parathyroid hormone), Forteo®, Bonsity (teriparatide), Tymlos® (abaloparatide)	

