Use of antipsychotics; n (%)	1,927 (28.5%)	108 (1.6%)	-0.009	103 (1.5%)	302 (2.2%)	-0.016	208 (1.5%)	410 (2.2%)	-0.288
Use of anxiolytics/hypnotics; n (%)	526 (7.7%)	601 (9.1%)	-0.001	719 (10.7%)	1,682 (12.0%)	-0.003	1,245 (9.2%)	2,283 (12.3%)	-0.032
Use of dementia meds; n (%)	219 (3.2%)	232 (3.5%)	-0.003	192 (2.9%)	680 (4.9%)	-0.010	411 (3.0%)	912 (4.9%)	-0.100
Use of antiparkinsonian meds; n (%)	171 (2.5%)	211 (3.2%)	-0.004	168 (2.5%)	543 (3.9%)	-0.008	339 (2.5%)	754 (4.1%)	-0.090
Use of Benzodiazepine; n (%)	886 (13.0%)	686 (10.4%)	0.008	1,280 (19.1%)	3,137 (22.4%)	-0.007	2,166 (16.0%)	3,823 (20.6%)	-0.119
All antidiabetic medications; n (%)	762 (11.2%)	565 (8.6%)	0.008	645 (9.6%)	1,525 (10.9%)	-0.004	1,407 (10.4%)	2,090 (11.3%)	-0.029
ACEI/ARB; n (%)	2,651 (38.9%)	2,178 (33.0%)	0.010	2,539 (37.9%)	5,556 (39.7%)	-0.003	5,190 (38.4%)	7,734 (41.7%)	-0.067
Use of Anticoagulants; n (%)	297 (4.4%)	407 (6.2%)	-0.008	284 (4.2%)	1,223 (8.7%)	-0.018	581 (4.3%)	1,630 (8.8%)	-0.183
Use of Amiodarone; n (%)	41 (0.6%)	39 (0.6%)	0.000	48 (0.7%)	146 (1.0%)	-0.003	089 (0.7%)	185 (1.0%)	-0.033
Digoxin; n (%)	89 (1.3%)	112 (1.7%)	-0.003	104 (1.6%)	302 (2.2%)	-0.004	193 (1.4%)	414 (2.2%)	-0.060
Use of Diuretics; n (%)	1,978 (29.0%)	1,794 (27.2%)	0.003	2,103 (31.4%)	4,693 (33.5%)	-0.004	4,081 (30.2%)	6,487 (35.0%)	-0.103
Use of Aspirin; n (%)	37 (0.5%)	42 (0.6%)	-0.001	59 (0.9%)	158 (1.1%)	-0.002	096 (0.7%)	200 (1.1%)	-0.042
NSAIDs (NOT including aspirin); n (%)	1,374 (20.2%)	1,156 (17.5%)	0.006	1,314 (19.6%)	2,998 (21.4%)	-0.004	2,688 (19.9%)	4,154 (22.4%)	-0.061
Hormone replace therapy; n (%)	558 (8.2%)	598 (9.1%)	-0.003	840 (12.5%)	1,682 (12.0%)	0.001	1,398 (10.4%)	2,280 (12.3%)	-0.060
Other Pressors; n (%)	45 (0.7%)	38 (0.6%)	0.001	66 (1.0%)	134 (1.0%)	0.000	111 (0.8%)	172 (0.9%)	-0.011

Use of Statins; n (%)	2,995 (43.9%)	2,448 (37.1%)	0.011	2,970 (44.4%)	6,633 (47.4%)	-0.004	5,965 (44.2%)	9,081 (48.9%)	-0.094
Prior bisphosphonate use; n (%)	1,625 (23.8%)	1,597 (24.2%)	-0.001	2,397 (35.8%)	5,368 (38.4%)	-0.004	4,022 (29.8%)	6,965 (37.5%)	-0.164
Healthcare Utilization Measures	1,020 (2010/1)	1,677 (= 11270)		_,_, (====,	2,222 (2211,2)		1,022 (271070)	*,, *** (* * * * * * * * * * * * * * * *	
Number of any prescribed drug									
mean (sd)	19.17 (16.44)	20.93 (19.56)	-0.097	19.38 (15.88)	25.07 (18.78)	-0.327	19.27 (16.16)	23.88 (19.01)	-0.261

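### Four exclusions look back 730 days, but only 450 days of enrolment are required, so eligibility on recent bisphosphonate or parathyroid hormone use depends partly on enrolment length

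*Protocol*

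**What the plan says.** Protocol Section 5.1 sets the entry requirement: patients are "required to have continuous enrollment during a baseline period of 450 days (15 months) before initiation" of zoledronic acid or the comparator. The design diagram in Section 4 uses a longer window for prior osteoporosis drugs: "EXCL: Prior use of Bisphosphonate OR parathyroid hormon Days [-730, 0". Appendix A repeats that window. Exclusion 1 (bisphosphonates) reads "Measured 730 days (2 years) prior to the day of drug initiation: Generic names: Alendronate, Ibandronate, Risedronate", and Exclusion 2.1 (parathyroid hormone and analogues) reads "Measured 730 days (2 years) prior to the day of drug initiation: Generic names: Brand names: Natpara". Exclusions 6 and 7 also use 730 days.

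Inclusion 2 admits women by an osteoporosis diagnosis or by older bisphosphonate use. The second route is "Measured time of enrollment to 730 days (2 years) prior to the day of drug initiation: Alendronate" and the other listed bisphosphonates. Appendix B, Table 1 has a baseline row "Prior bisphosphonate use; n" (%). The protocol does not define that variable or say how unobserved history is coded. The general covariate window in the design diagram is days −450 to 0.

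**The concern.** An exclusion can only act on time that the database records. If a woman entered the plan 500 days before index, a bisphosphonate dispensed 600 days before index is invisible. She passes Exclusion 1, while an otherwise identical woman with three years of history fails it. Part of the eligibility rule is then decided by length of enrolment and not by treatment history.

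This matters because bisphosphonates and parathyroid hormone analogues are themselves osteoporosis treatments, and the outcome is hip fracture. The baseline variable meant to describe older bisphosphonate use has a related weakness. If it can only be filled from before day −730, a woman with less history is recorded as a non-user whatever she took. Enrolment length is not among the covariates listed in Table 1, so the propensity score does not balance it directly.

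**Working it through.** **1. The windows side by side.**
- Required continuous enrolment: 450 days (Section 5.1).
- Exclusions 1, 2.1, 6 and 7: 730 days (Appendix A; also Section 4 for the drug exclusions).
- Rule requiring 730 days of enrolment: none found.
- Largest unobserved part of the exclusion window: 730 − 450 = 280 days; 280/730 = 38%.

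**2. How much work each exclusion does** (flowchart, Section 5.3; Optum first, then MarketScan).
- Exclusion 1: 6,854/26,577 = 25.8%; 10,259/40,721 = 25.2%; together 17,113/67,298 = 25.4%.
- Exclusion 2.1: (305 + 814)/(19,723 + 30,462) = 1,119/50,185 = 2.2%.
- Exclusion 6: 4 + 5 = 9 women. Exclusion 7: 43 + 65 = 108 women.

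The practical issue is therefore Exclusion 1. The 25.4% counts any use in the time that could be seen, including recent use. It does not estimate use confined to the unseen days.

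**3. The covariate** (Appendix B, Table 1, unmatched, raloxifene then zoledronic acid).
- Optum: 1,625/6,815 = 23.8%; 1,597/6,605 = 24.2%.
- MarketScan: 2,397/6,694 = 35.8%; 5,368/13,997 = 38.4%.

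These women remain after users in the last 730 days were removed. Unless the covariate covers agents outside the exclusion list, the yes answers cannot come from the 450-day covariate window. They must come from before day −730, which matches the drug route of Inclusion 2. A woman with 450 to 729 days of history has no such time. Each percentage uses the whole arm as denominator and there is no unknown row, so every woman who is not yes is counted with the no group.

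**4. What bounds the number affected.** On this reading, every yes proves observable time before day −730. The yes count is 1,625 + 1,597 + 2,397 + 5,368 = 10,987 of 13,420 + 20,691 = 34,111, or 32.2%. At most 67.8% of the unmatched cohort can then have less than 730 days of history. The lower bound is zero. The bound loosens further if data from an earlier enrolment spell are used. No narrower figure follows from the protocol.

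**5. What a run restricted to 730 days would cost.** The plan's own power comes first. Section 10 gives 18,028 × 10.40/1,000 = 187.49 events and power 0.9508 at HR 0.59. With power = Φ(½·√d·|ln HR| − 1.96), ½·√187.49 × 0.5276 − 1.96 = 1.652 and Φ = 0.9508, which agrees. The share of women lost is an assumption, applied equally to both arms with unchanged risk:

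| Assumed loss | Events | Power at HR 0.59 | Power at HR 0.745 |
|---|---|---|---|
| 0% | 187.5 | 0.951 | 0.522 |
| 10% | 168.7 | 0.929 | 0.481 |
| 20% | 150.0 | 0.898 | 0.438 |
| 40% | 112.5 | 0.799 | 0.345 |

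HR 0.745 is the protocol's own 18-month trial estimate (Section 1.6).

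**The case against.** The best defence is that the design deliberately uses all history available. Osteoporosis diagnosis and amputation are searched from start of enrolment, and a 730-day exclusion with a 450-day minimum removes more users than a 450-day exclusion would. That is fair, and it is a reason to leave the primary entry rule alone. It does not remove the dependence on enrolment length, which the protocol neither states nor tests. A lookback sensitivity analysis could sit in an analysis plan not seen here, and the coding of the covariate could be set out in the external folder that Appendix A mentions. The coding point is accordingly an inference.

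The effect may also be small. Suppose 721 matched women were wrongly retained, all in one arm (8% of 9,014), and such use halved the hazard. The hazard ratio would move by about 0.08 × 0.5 = 4%; with an equal split it would hardly move. These inputs are assumptions, but they show that a large bias should not be presumed. Calendar period, a partial proxy for available history, is already marked as a propensity score variable.

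Three stronger readings are tempting and not supported:
- **A contradiction with Section 5.2.** The phrase "To keep the amount of lookback available in the 2 treatment groups equal" explains why the new-use washout is 450 days for both drugs. That aim is met. It does not promise equal total history for every exclusion.
- **The matched imbalance as evidence.** Prior bisphosphonate use appears to be 31.3% against 34.3% after matching (pooled standardised difference −0.0639). That row is identified by position, since its label and any star marking model inclusion are not legible in the text available. Legible starred rows mostly lie within about 0.03, while unstarred rows such as venous thromboembolism (−0.0534) look more like this one. The gap may only mean that the variable was left out of the score.
- **A differential error.** No figure on enrolment length by arm is given.

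**Conclusion.** The mismatch stands as written: 450 days are guaranteed, 730 are searched, and up to 280 days go unobserved for women with 450 to 729 days of history. Eligibility on recent bisphosphonate or parathyroid hormone use therefore depends partly on enrolment length. The consequence for the covariate is a strong inference from its prevalence and denominators, not a stated rule.

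The number of women affected and the size and direction of any bias cannot be computed from the protocol. A reader might multiply assumed shares: 10% to 40% of women with short history and 2% to 10% of those with use only in the unseen days give 0.10 × 0.02 × 18,028 = 36 to 0.40 × 0.10 × 18,028 = 721 matched women. Neither input has a source, so the range is an illustration and not a finding. The point is a worthwhile, inexpensive improvement; nothing here shows the primary result to be biased.

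**What to change.** - Report continuous pre-index enrolment by arm in Table 1, before and after matching, in each database.
- Add it in categories (for example 450–729, 730–1,094, and 1,095 days or more) to the propensity score in each database.
- Prespecify a sensitivity analysis of the primary outcome in women with at least 730 days of continuous enrolment. The four 730-day exclusions are then fully observed.
- Define the prior-bisphosphonate covariate and its window, with a separate category for women who have no observable time before day −730. The restricted run does not do this job: a woman with exactly 730 days still has no time before day −730.

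The primary 450-day entry rule stays. The cost is one covariate, one table row, one recoded variable and one extra run. Matched numbers may shift slightly, and the restricted run will have fewer events and less power, as tabulated above. The date of the comparative analyses in Section 13 is blank, so on this document the changes can still be prespecified.

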5.2 Important steps for cohort formation

New use of zoledronic acid (exposure) is defined as no use of the exposure drug in the 450 days prior to index date. New users of zoledronic acid will be allowed to receive concomitant therapy with raloxifene before and/or during the study period, similar to the trial. We use the long look-back period of 450 days to define new use because zoledronic acid is given as a yearly infusion; thus, a identifying whether a patient has current zoledronic acid exposure requires at least 365 days of look back. We extended this lookback to 450 days (approximately 15 months) to allow for patients who have a short gap between infusions. To keep the amount of lookback available in the 2 treatment groups equal, New use of raloxifene (comparator, proxy to placebo) was also defined as no use of either exposure or comparator drugs in the 450 days prior to index date.

5.2.1 Eligible cohort entry dates

Zoledronic acid indication for treatment of postmenopausal women with osteoporosis was approved by FDA on Aug 20, 2007.

- IBM® MarketScan®: Aug 21, 2007 December 31, 2018 (end of available data)
- Optum CDM: Aug 21, 2007 Mar 31, 2020 (end of available data)

5.2.2 Specify inclusion/exclusion criteria for cohort entry and define the index date Inclusion and exclusion criteria were adapted from the trial as closely as possible. Definitions for all inclusion/exclusion are provided in **Appendix A** and are summarized in the flowcharts below.

5.3 Flowchart of the study cohort assembly

For zoledronic acid vs. raloxifene

	Optı	ım CDM	IBM® Ma	rketScan®
	Excluded Patients	Remaining Patients	Excluded Patients	Remaining Patients
All patients		77,673,639		200,203,908

	-77,476,067	197,572	-	489,107
Did not meet cohort entry criteria			199,714,801	
Excluded due to insufficient enrollment	-52,317	145,255	-164,242	324,865
Excluded due to prior use of referent	-81,791	63,464	-185,458	139,407
Excluded due to prior use of exposure	-9,268	54,196	-29,153	110,254
Excluded because patient qualified in >1 exposure category	-1	54,195	-1	110,253
Excluded based on Inclusion #1 - Age, range 65-89 years	-17,914	36,281	-58,739	51,514
Excluded based on Inclusion #2 - Gender, female [Excluded if Male or Unknown]	-6,080	30,201	-6,857	44,657
Excluded based on Inclusion #3 - Osteoporosis	-3,624	26,577	-3,936	40,721
Excluded based on Exclusion #1 - Oral bisphosphonate use	-6,854	19,723	-10,259	30,462
Excluded based on Exclusion #2.1 - PTH or PTH analogue use	-305	19,418	-814	29,648
Excluded based on Exclusion #2.2 - Anabolic–androgenic steroids (AAS) and	-10	19,408	-32	29,616
growth hormones (GH)				
Excluded based on Exclusion #2.3 - Glucocorticoids use	-1,352	18,056	-1,697	27,919
Excluded based on Exclusion #3 - CCI (180 days) >=10	-196	17,860	-154	27,765
Excluded based on Exclusion #4 - Malignant neoplasm, excluding non-melanoma	-2,461	15,399	-4,141	23,624
skin cancer				
Excluded based on Exclusion #5 - Disorders that influence bone metabolism	-1,426	13,973	-2,235	21,389
Excluded based on Exclusion #6 - Glucocorticoid-Induced Osteoporosis	-4	13,969	-5	21,384
Excluded based on Exclusion #7 - Paget's Disease	-43	13,926	-65	21,319
Excluded based on Exclusion #8 - Alcohol abuse or Drug addiction or Non-	-141	13,785	-137	21,182
compliance	1	10.504	2	21 170
Excluded based on Exclusion #9 - Pregnancy	-1	13,784	-3	21,179
Excluded based on Exclusion #10 - Lower extremity amputation	-18	13,766	-37	21,142
Excluded based on Exclusion #11 - Denosumab use	-53	13,713	-35	21,107
Excluded based on Exclusion #12 - Zoledronic Acid use (for raloxifene users)	-223	13,490	-313	20,794
Excluded based on Exclusion criteria #13 - End-stage renal disease	-5	13,485	-12	20,782
Excluded based on Exclusion criteria #14 - End-stage liver disease	-33	13,452	-66	20,716
Excluded based on Exclusion criteria #15 - Blindness or low vision	-32	13,420	-25	20,691
Excluded based on Exclusion criteria #16 - Abaloparatide	-0	13,420	-0	20,691
Excluded based on Exclusion criteria #17 - Romosozumab	-0	13,420	-0	20,691
Final cohort		13,420		20,691

6. Variables

6.1 Exposure-related variables:

Study drug:

The study exposure of interest is new initiation of zoledronic acid 5 mg, IV administered annually. New initiation will be defined by no use of zoledronic acid in the prior 15 months (450 days) before treatment initiation (washout period).

Comparator agents:

Primary analysis:

- New initiators of raloxifene, oral tablet administered daily. New initiation will be defined by no use of raloxifene and zoledronic acid in the prior 15 months (450 days) before treatment initiation (washout period).

Secondary analysis:

- Non-user comparator (risk-set sampled cohort).

6.2 Preliminary Covariates:

- Age
- Combined Comorbidity Index (CCI), measured over the baseline covariate assessment period, defined as 180 days prior to and including index date.

Covariates listed above represent only a small subset of covariates that will ultimately be controlled for in the design and analysis. We use the covariates above only for initial feasibility analyses to judge whether there is likely to be sufficient overlap between treatment groups to proceed with the study. Remaining covariates are defined only after the study has passed the initial feasibility analysis and the initial power assessment and are listed in Table 1 (**Appendix B**). Gender is not included since the study is already restricted to female subjects.

6.3 Outcome variables and study follow-up:

